7.6 Determination of Sample Size

The primary endpoint of the study is time to first occurrence of disease reactivation (including full and partial disease reactivation) during the RW phase of the study. There is limited historical data for this disease condition, for either a control or an experimental test product, however the frequent recurrence of disease reactivations was expected in the control arm ([Wada 2014](#)). Originally, an 8-week event rate is assumed to be 90% in the placebo group and a considerable reduction in disease reactivations for patients receiving TA was expected. However, a lower event rate was observed from the currently enrolled (still blinded) patients. Thus, the RW phase is prolonged to a maximum of 16 weeks to better assess the effect of TA withdrawal. The power calculations below will assume the same 90% event rate in the SOC arm at 16 weeks. [Figure 1](#) below displays the power achieved for a two-arm study and assumes the following:

- Two-sided log-rank test, with input based on the proportion of patients surviving (ie, event-free) at 16 weeks
- Two-sided alpha = 0.05
- A 1:1 randomization of 10 patients (ie, 5 patients per arm)
- The proportion of patients surviving (ie, event-free) in the control arm at Week 16 of the RW phase is 0.1, which equates to a 90% event rate
- No patients in either group drop out of the study prior to experiencing a disease reactivation or completing the 16 week treatment period as planned
- Total study time is 32 weeks, including a 16-week accrual period and a 16 week follow-up time
- Varying levels of a hazard ratio, from 0.1 to 0.25 in 0.05 increments

Figure 1 Power vs. Hazard Ratio

A hazard ratio of 0.1 equates to an assumed 16-week event rate in the TA group of 20.6% (ie, a survival event-free rate of 79.4%). These assumptions achieve 78.4% power based on a two-sided log rank test with an overall sample size of 10 patients to be randomized in the RW phase (5 in the placebo group and 5 in the TA group). A hazard ratio of 0.1 results in an assumed number of total events among 10 patients to be 6.7, with 4.9 occurring in the placebo group and 1.8 occurring in the TA group.

No power calculations were performed for the SAOL phase of the study, as analysis will be descriptive in nature.

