16.3 Sample Size Calculations

[figure not shown]
Power Calculations

The primary endpoint of the study is time to first occurrence of disease reactivation (including full and partial disease reactivation) during the RW phase of the study. There is limited historical data for this disease condition, for either a control or an experimental test product, however the frequent recurrence of disease reactivations was expected in the control arm (Wada 2014). Originally, an 8-week event rate was assumed to be 90% and a considerable reduction in disease reactivations for subjects receiving Tadekinig alfa was expected. However, a lower event rate was observed from the currently enrolled (still blinded) patients. Thus, the RW phase is prolonged to a maximum of 16 weeks to better assess the effect of Tadekinig alfa withdrawal. The power calculations below will assume the same 90% event rate in the SOC arm at 16 weeks.

Figure 2 below displays the power achieved for a two-arm study and assumes the following:

- Two-sided log-rank test, with input based on the proportion of patients surviving (i.e., event-free) at 16 weeks;
- Two-sided alpha = 0.05;
- A 1:1 randomization of 10 patients (i.e., 5 patients per arm);
- The proportion of patients surviving (i.e., event-free) in the control arm at Week 16 of the RW phase is 0.1, which equates to a 90% event rate;
- No patients in either group drop out of the study prior to experiencing a disease reactivation or completing the 16-week treatment period as planned;
- Total study time is 32 weeks including a 16 week accrual period and a 16 week follow-up time;
- Varying levels of a hazard ratio, from 0.1 to 0.25 in 0.05 increments.

Figure 2 Power vs. Hazard Ratio

A hazard ratio of 0.1 equates to an assumed 16-week event rate in the Tadekinig alfa group of 20.6% (i.e., a survival event-free rate of 79.4%). These assumptions achieve 78.4% power based on a two-sided log rank test with an overall sample size of 10 subjects to be randomized in the RW phase (5 in the placebo group and 5 in the Tadekinig alfa group). A hazard ratio of 0.1 results in an assumed number of total events among the 10 subjects to be 6.7, with 4.9 occurring in the placebo group and 1.8 occurring in the Tadekinig alfa group.

No power calculations were performed for the SAOL phase of the study, as analysis will be descriptive in nature.

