7.4.2.1 Primary Estimand of the Primary Efficacy Endpoint

The primary estimand for the primary endpoint will be described as follows:

Population: All patients in the RW-FAS population.

Endpoint: Time to first occurrence of disease reactivation during the RW phase.

Intercurrent events:

- End of RW phase: patients who do not experience a disease reactivation and complete the RW phase will be censored at the time of their last disease assessment during the RW phase regardless of the length of the RW phase (according to the protocol version the patient was treated under).
- Rescue immunosuppression treatment: patients who receive rescue immunosuppression treatment without objective disease reactivation and continue in the RW phase will be censored at the time of their last disease assessment during the RW phase, including assessments up to the start day of the rescue immunosuppression treatment.
- Clinical signs of inflammation that are not disease related: patients who present with clinical or laboratory signs of inflammation meeting the criteria of disease reactivation that are determined by the treating physician to be related to an infection rather than disease reactivation and are resolved after repeat assessments within the visit window will not be considered to have a disease reactivation at that visit (see [Section 7.4.2.2](#)).

Population-level summary: Kaplan-Meier (KM) estimates of the survival curves by treatment group, hazard ratio including 95% CI, and log-rank test.

The primary efficacy analysis will test the following hypothesis:

- H_0 : The survival distribution of time to first occurrence of disease reactivation during the RW phase is equal between TA and placebo
- H_1 : The survival distribution of time to first occurrence of disease reactivation during the RW phase is different between TA and placebo

TA will be compared to placebo using the log rank test. Kaplan-Meier (KM) estimates of the distribution of time-to-event will be summarized and graphed by treatment group. Greenwood's formula will be used to estimate the standard error of the KM statistic. The

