7.4.2.3 Sensitivity Analyses of the Primary Efficacy Endpoint

The primary endpoint analysis will be repeated on the RW-PPAS, provided the RW-FAS and RW-PPAS differ by at least one patient.

In addition, the following tipping point analyses will be performed for the primary endpoint to assess the impact of the different lengths of the RW phase due to the different versions of the protocol. For patients enrolled in protocol versions 4.0/4.1 and earlier whose planned RW duration was only 8 weeks and had no disease reactivation during the RW phase:

1. A worst-case imputation will be applied to patients in both treatment groups by assigning patients as having disease reactivation at the next day after the last per protocol visit.
2. A best-case imputation will be applied to patients in both treatment groups by assigning patients as not having disease reactivation until Week 16 of the RW phase.
3. A worst-case imputation will be applied to patients in the TA treatment group and a best-case imputation will be applied to patients in the Placebo treatment group.

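### The stated 78.4% power assumes that every patient has a full 16-week RW phase, but the primary analysis pools patients whose RW phase was planned for 8 weeks; each two of them cost about 3 to 5 points of power at HR 0.1

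*SAP*

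**What the plan says.** **Power.** SAP 7.6 specifies a "Two-sided log-rank test, with input based on the proportion of patients surviving (ie, event-free) at 16 weeks", with "Two-sided alpha = 0.05" and five patients per arm. The event-free proportion "in the control arm at Week 16 of the RW phase is 0.1, which equates to a 90% event rate". No patient is assumed to leave before a reactivation or "completing the 16 week treatment period as planned". The calculation also enters a total study time of 32 weeks (16 accrual plus 16 follow-up). For HR 0.1 it reports 78.4% power and 6.7 events: 4.9 on placebo and 1.8 on Tadekinig alfa (TA). Protocol 16.3 gives the same inputs and results.

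**RW length.** SAP 6.1.5 says the RW phase was 8 weeks in the original design and became 16 weeks from version 5.0. Protocol 16.3 gives the reason, a lower event rate than expected in patients already enrolled: "Thus, the RW phase is prolonged to a maximum of 16 weeks to better assess the effect of Tadekinig alfa withdrawal".

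**Analysis.** SAP 7.1.6 combines original-design patients who were randomised to TA in the initial double-blind (RDBPC) phase with later patients for all analyses. SAP 7.4.2.1 says that patients who complete the RW phase without a reactivation "will be censored at the time of their last disease assessment during the RW phase regardless of the length of the RW phase". SAP 7.4.2.3 adds three imputation analyses for event-free patients from versions 4.0/4.1 and earlier "whose planned RW duration was only 8 weeks".

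**The concern.** The SAP was adapted to the 8-week patients in the estimand, the per-protocol set, the carry-forward rules and the sensitivity analyses, but not in the sample-size section. Under the plan's constant hazard, a placebo patient observed for 8 weeks has a 68.4% chance of a reactivation, not 90%. Fewer events means less power.

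About five events are expected in total, so a non-significant result is quite possible even if the drug works as assumed. Readers would judge such a result against 78.4%, a figure that belongs to a data set the SAP does not analyse.

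**Working it through.** **Inputs (SAP 7.6).** 5 v 5 patients, two-sided alpha 0.05, placebo event-free proportion 0.1 at 16 weeks, HR 0.1. The 8-week RW length is from SAP 7.4.2.3. The number of 8-week patients is not given, so 0, 2, 4 and 6 of 10 are assumed, split evenly between arms.

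**Event probabilities.** Placebo hazard = −ln(0.1)/16 = 0.1439 per week; TA hazard = 0.01439.

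| Follow-up | Placebo | TA |
|---|---|---|
| 8 weeks | 1 − 0.1^0.5 = 68.4% | 1 − 0.1^0.05 = 10.9% |
| 16 weeks | 90% | 1 − 0.1^0.1 = 20.6% |
| 32 weeks | 1 − 0.1² = 99% | 1 − 0.794² = 36.9% |

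**Reproducing the plan's figure.** Power was computed by a Lakatos-type log-rank formula and by log-rank simulation.

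| Follow-up for all 10 | Events (placebo + TA) | Lakatos | Simulation |
|---|---|---|---|
| 32 weeks each | 4.95 + 1.85 = 6.80 | 77.5% | 80.4% |
| 16-week uniform accrual, then 16 weeks | 4.80 + 1.45 = 6.26 (rounded) | 74.6% | not run |
| 16 weeks each | 4.50 + 1.03 = 5.53 | 68.5% | 70.4% |

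Only the first row comes close to both the 78.4% and the 4.9 + 1.8 events. Schoenfeld's formula at 16 weeks gives 77.3%, but with 5.5 events, so it is not the plan's calculation. The starting point for the effect of the 8-week patients is therefore the 16-week row, about 70%.

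**Effect of 8-week patients.** With k such patients per arm, expected events are:
- placebo: (5 − k)(0.900) + k(0.684)
- TA: (5 − k)(0.206) + k(0.109)

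For k = 2: placebo 3(0.900) + 2(0.684) = 4.07; TA 3(0.206) + 2(0.109) ≈ 0.83; total 4.90.

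The simulations used 200,000 trials per scenario, exponential times, HR 0.1 and the chi-square log-rank test, counting success only in favour of TA. Visit-detected means that reactivation is found at RW Weeks 2, 4, 8, 12 or 16.

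| 8-week patients of 10 | Events | Continuous times | Visit-detected | Lakatos |
|---|---|---|---|---|
| 0 | 5.5 | 70.3% | 70.3% | 68.5% |
| 2 | 5.2 | 67.4% | 66.1% | 65.0% |
| 4 | 4.9 | 62.3% | 60.1% | 61.2% |
| 6 | 4.6 | 59.4% | 56.6% | 57.1% |

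Repeat simulations agreed to within about a point.

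**Loss per pair at HR 0.1.** The simulated cumulative losses are 2.9–4.2, 8.0–10.2 and 10.9–13.7 points for two, four and six patients. Dividing by one, two and three pairs gives 2.9–4.2, 4.0–5.1 and 3.6–4.6, so about 3 to 5 on average. Single steps are uneven because the test is discrete at this size. Lakatos gives 3.5, 3.8 and 4.0 for successive pairs; Schoenfeld gives 2.4 to 3.3.

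**HR 0.25.** Simulated power falls from about 40% with no 8-week patients to 34–36% with four, or 2 to 3 points per pair. Lakatos gives 41.9%, 39.5% and 37.0% for none, two and four.

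**The case against.** **The analysis already allows for unequal RW lengths.** This is largely true. Censoring is pre-specified, the per-protocol set is adapted, and SAP 7.4.2.3 examines the different lengths. A reader might infer that the primary test is biased. The documents do not support that: the cut-off is set by protocol version, not by outcome or arm, and the log-rank test accommodates it. What remains is that none of these provisions corrects the stated power.

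**The number of 8-week patients is unknown.** This stands. SAP 6.1.5 reports three patients under the original design, of whom only those given TA in the RDBPC phase are pooled, and some may have stopped early. The number under 4.0/4.1 is not stated. The size can only be a range.

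**Ten is a minimum.** SAP 6.1 expects at least 10 randomised from up to 15 enrolled. With a 16-week cap and HR 0.1, 12 randomised including two 8-week patients gives 75%, and 14 including four gives 80%. This stands, and it is a reason to recalculate with the actual number.

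**It overlaps with the 32-week input.** Both are corrected in the same paragraph, but they are separate. The loss shown here is measured from the 16-week figure and remains after the 32-week input is put right.

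**Conclusion.** The point holds. The 78.4% describes neither a 16-week trial of 10 patients (about 70%) nor the pooled data that will be analysed (about 56–68% if two to six of the 10 have an 8-week cut-off). These figures rest on constant hazards, HR 0.1, a 90% placebo event rate at 16 weeks, no dropout, and an even split of the 8-week patients. If two such patients fall in one arm, Lakatos gives 64.3% (both TA) or 63.5% (both placebo), a loss of 4 to 5 points instead of 3.5.

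Three stronger readings should be avoided:
- A reader might take the plan's assumption at face value and infer that 78.4% is the power at 16 weeks of follow-up. The event counts contradict this; they match about 32 weeks.
- A reader might then attribute the whole gap below 78.4% to the 8-week patients. About 9 to 10 points of it come from the excess follow-up.
- A reader might infer a steady 5 points per pair. That is the upper end at HR 0.1. Under Lakatos, losses near 5 points for the first two pairs (4.6 and 5.2) arise only if the other patients keep 32 weeks.

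The consequence is for interpretation of the result. The test, the estimate and the sample size are unaffected.

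**What to change.** In SAP 7.6, correct the 32-week input and in the same step restate expected events and power for HR 0.1 to 0.25 by simulating the planned log-rank test. Cap each RW-FAS patient's follow-up at 8 or 16 weeks, according to the protocol version under which the patient was treated. Use the actual number randomised, and state how many had 8 weeks.

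The version at enrolment does not by itself settle the count. SAP 7.4.2.1 ties RW length to the version of treatment, while SAP 7.4.2.3 refers to the version of enrolment, so the text should settle on one. For original-design patients, the RDBPC assignment decides who is pooled; the RW assignment is not needed and should not be used.

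The cost is one rewritten paragraph and a short simulation. No patients are added and no analysis changes. The downside is a less favourable stated power.

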7.7 Changes in the Conduct of the Study or Planned Analyses

Changes to the planned analyses relative to what was outlined in the clinical study protocol (Version 6.0) include the following:

- A description for how to handle situations where clinical or laboratory signs of inflammation meeting the criteria of disease reactivation for the primary endpoint are present but are determined by the treating physician to be related to an infection rather than disease reactivation and are resolved after repeat assessments within the visit window, has been added to Section 7.4.2.2, but is not included in the clinical study protocol.
- A correction to the RW Per-Protocol Analysis Set (RW-PPAS) listed in the protocol is included below.

The study under the original protocol and through Amendment 2 of the protocol (Version 3.0) was designed with an 18-week RDBPC phase, followed by an 8-week RW phase for further efficacy and safety evaluation. Three patients were enrolled in the study under these protocol versions and each either completed the RDBPC phase and RW phase or

terminated the study early. As described in [Section 7.1.6](#), patients randomized to the TA group during the RDBPC phase of the original study design will be included in analyses for the updated study design, to be combined with those patients enrolled under Amendment 4 (Version 4.0) and any subsequent amendments. Protocol version 5.0 and subsequent amendments extended the RW phase from 8 weeks with last the RW visit at Week 26 [V11] to 16 weeks, with the last RW visit at Week 34 [V13]. Accordingly, the RW Per-Protocol Analysis Set (RW-PPAS) is adapted to include all patients in the RW-FAS who complete the RW phase up through Week 26 (V11) for protocol version 4.0/4.1 or Week 34 (V13) for protocol versions 5.0 and 6.0 or have disease reactivation and for whom no relevant protocol deviations were documented.

Protocol version 5.0 and subsequent amendments identify response to therapy during the SAOL phase as a key secondary endpoint. However, since this key secondary endpoint is only being presented descriptively without any statistical testing, it is not included in the hierarchical list for fixed-sequence testing described in [Section 7.4.5.5](#).

[Appendix A](#) includes a description of the mapping of the mAIDAI components into the Objective mAIDAI total score.

APPENDIX A

Objective mAIDAI total score mapping:

mAIDAI score		Objective mAIDAI components for efficacy evaluation	
	Score		Score
Fever > 100.4	 0 (No) -  1 (Yes)	Fever > 100.4	 1 (Yes)
Abdominal Pain / Colic	 0 (No) -  1 (Yes)		
Nausea / Vomiting	 0 (No) -  1 (Yes)		
Diarrhea	 0 (No) -  1 (Yes)	Diarrhea	 1 (Yes)
Transaminitis	 0 (No) -  1 (Yes)	Transaminitis and/or hepatomegaly	 1 (Yes)
Organomegaly If yes, specify  Hepatomegaly  Splenomegaly  Adenopathy	 0 (No) -  1 (Yes)	Splenomegaly and/or adenopathy	 1 (Yes)
Rash	 0 (No) -  1 (Yes)	Rash	 1 (Yes)
Uveitis 3+ / 4+	 0 (No) -  2 (Yes)	Uveitis	 1 (Yes)
Uveitis 1+ / 2+	 0 (No) -  1 (Yes)		
Arthralgia	 0 (No) -  1 (Yes)	Arthritis	 1 (Yes)
Arthritis	 0 (No) -  1 (Yes)	Radiologic CNS Involvement	 1 (Yes)
Radiologic CNS Involvement	 0 (No) -  1 (Yes)		
CNS Symptoms	 0 (No) -  1 (Yes)		
Cytopenia (HgB < 9.0, PLT < 100, WBC < 3.0)	 0 (No) -  1 (Yes)	Cytopenia (HgB < 9.0, PLT < 100, WBC < 3.0)	 1 (Yes)
mAIDAI Score at this visit (total sum of all scores from each category above):		Number of affected end organs = objective mAIDAI components:
